UAB Research Pharmacy
UAB Hospital Investigational Drug Service Pharmacy
[name]
[name]
[contact]
[contact]

Changes between Amendment 11 version 2.8 dated 20 Jan, 2021 and Amendment 12 version 2.9 dated 20 Sep 2021

Section/location	Change	Rationale
8	
 • Adding an unscheduled visit 	Administrative change
Study synopsis	
 • In a previous amendment it was stated that 4-20 participants are to be enrolled and treated in addition to the first 4 in the seed model (Section 4.1.2). The enrollment number is being increased to 24 to clarify that the previously stated 4-20 participants are in addition to the first 4. 	Administrative change

STUDY SYNOPSIS

Objective:	To obtain safety information in small cohorts of individuals (three patients per group), with cohorts to receive escalating doses of M032. Safety will be assessed at each dose level before proceeding to the next dose. Biologic secondary objectives include characterization of the in situ activity of M032 after intratumoral inoculation and of the local and systemic immune responses to M032. As a clinical secondary objective, patients will be followed serially by MRI for potential clinical response to M032. The clinical strategy takes advantage of the virus' ability to infect and lyse tumor cells and the potential for enhancement of this effect by the induction of an anti-tumor immune response by IL-12 as well as an anti-angiogenic response by this cytokine.
Treatment Indication:	Progressive growth of glioblastoma multiforme , anaplastic astrocytoma or gliosarcoma after radiation therapy.
Clinical Phase:	Phase 1 (open-label)
Design:	Single dose of M032 infused through catheters into region(s) of tumor defined by MRI; Up to 3 patients/dosage level; dosage escalation proceeds only after a minimum of 24 days of observation, if incidence of Grade III/IV toxicities is acceptable. Dose increases or reductions will be determined using a modified Continual Reassessment Method (CRM); extent of dose changes for subsequent subjects will be increased up to, but not exceeding the next higher dose level (1 log). Dose modifications will utilize a modified CRM for each successive subject until an MTD or the maximal planned dose is reached.
Study Duration Per Patient:	12 months

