4.1.1 Continual Reassessment Method

[name] and [name], Professors in the Department of Biostatistics, UAB School of Public Health, with expertise in CRM calculations will apply the software developed by [name], (Cedars-Sinai) who will serve as a clinical trial statistical consultant to advise and assist in the implementation of the Continual Reassessment Method in determining dose alterations. In addition, Drs. [name] and [name], will provide support in clinical trial and data management, and data analysis.

Rationale for the Use of a Modified Continual Reassessment Method: The description of the determination of MTD from the CRM that we are employing is adapted from that used previously in a Phase I/II study of the poly (ADP-ribose) polymerase-1 (PARP-1) inhibitor BSI-201 in patients with newly diagnosed malignant glioma conducted under the New Approaches to Brain Tumor Therapy (NABTT) CNS Consortium. To estimate the MTDs in terms of clinical toxicities, a modified continual reassessment method (CRM), based on that described by Piantadosi et al [45], will be employed. The CRM has been shown to be less biased and more efficient for estimating the MTD than traditional dose-finding models. The efficiency of the CRM stems from its explicit use of biological knowledge in the form of a parametric dose toxicity model. In the CRM, only a starting dose is specified and the dose is escalated or deescalated based on the toxicities of the previous cohort.

This is advantageous because the investigators can choose the next dose level based on all available clinical and statistical information rather than on relatively arbitrary predetermined doses. One disadvantage of the CRM is uncertainty of the dose levels that will be used in the trials, because the specific dose levels are not defined at the start of the trial.

Details of CRM Design: The primary statistical outcome for this study is the occurrence of serious clinical toxicity. Investigators would like to employ a dose of drug that yields approximately a 1/3 chance of serious toxicity. In our opinion, this represents the best chance at a beneficial therapeutic ratio for this unusually difficult disease to treat. This target probability of toxicity is chosen based on knowledge of previous trials of oHSV in

glioma, but is fundamentally subjective. The relationship between dose of drug and probability of toxicity is assumed to follow a two-parameter logistic model, both before and during the dose finding given by:

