Three values for d_{90} will be chosen in this protocol with weights of one tenth that of real subject data. This allows flexibility in the upper end of the dose toxicity curve. This adaptation to the CRM came about after subject data demonstrated that d_{90} was incorrect in previous studies, because doses approaching d_{90} were tried with no toxicities observed. This situation required that d_{90} be moved to a higher dose or the fitted dose toxicity curve became too steep and no dose escalations resulted.

We assume the dose for $d_{10} = 1 \times 10^4$ pfu for M032 (**Table 1**). A set of three values will be chosen for $d_{90} = 1 \times 10^{15}$ pfu. These values for d_{90} spread probability mass over a wider range and may eliminate the need to increase d_{90} if the data are inconsistent with a single value. Based on these starting points, our desire is to employ a dose of virus to yield no more than 33% chance of clinical toxicity. The initial starting dose will be assumed to be 1×10^5 PFU and the maximum dose to be tested would be 1×10^9 PFU. Further assumptions would be that the maximum number of subjects would be 204 and that the dose cohort size would be 1. Further, the next CRM recommended log dose would be rounded to the nearest 0.5 or full dose. Moreover, the number of consecutive subjects at the maximum tolerated dose would be 10 or a number until 20 subjects are treated, whichever comes first. This will allow us to collect more information of the safety of the MTD. If a second toxicity is observed for patients on the highest dose, then the next lower dose is used and declared MTD if 10 consecutive subjects on the same dose are toxicity free or if n=20 is reached. If more toxicities are found, CRM will be used in the de-escalation of the dose.

The outcome space for the first CRM iterations would look like the values shown as six sample scenarios in **Table 2** using a starting dose 1×10^5 pfu. We will not allow dose escalations to exceed 10 times the maximum dose already administered. In this way, we prevent a too rapid dose escalation or testing high doses without a reasonable degree of certainty concerning their safety. Although the values in **Table 2** appear reasonable to us currently, we emphasize that they should not be taken literally. Indeed, if we receive approvals (DSMB, IRB, FDA), we will update the CRM model using the four patients previously enrolled and treated. Some of the data

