11. STATISTICAL CONSIDERATIONS

We will implement the CRM design (the dosing range is described previously in this protocol) in a manner similar to that of Geletneky et al. [43] We will define the primary criterion for dose modification as the relative frequency of a DLT at a given dose level. A dose will be considered as tolerable if the probability of toxicity is ≤33%. The Recommended Phase 2 Dose (RP2D) will be the dose level with the highest posterior probability of having a toxicity of ≤33%. The Optimal Biologic Dose (OBD) will be the RP2D that is obtained by enrolling the fewest number of evaluable patients possible. The posterior probability for toxicity will be determined using a logistic model, where the toxicities will be parameterized as probabilities in the model. When a patient enters the study, the dose level will be determined by calculating the posterior probability for each dose level to be tolerable. The highest dose level that is tolerable will be allocated. Regarding the dose escalation scheme, a conventional three-at-one [44] design will be used as long as no DLT is observed. After the first DLT is observed, one additional patient will be enrolled at the same dose before the dose will be determined as the RP2D using the logistic model. The highest dose with a median probability of at least 33% will be applied as the current RP2D to the subsequent patient, following the CRM [45]. If the RP2D is calculated as dose level -1 (i.e. 1×10^4 PFU), the trial will end with no safe dose established.

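### Section 11 repeats the dose that caused the first DLT before the model is used, which can conflict with its own ≤33% allocation rule and with the one-patient CRM of Section 4.1.1

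*Combined protocol and SAP*

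**What the plan says.** Section 11 contains three instructions that bear on the patient who follows the first DLT:

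- The limit: "A dose will be considered as tolerable if the probability of toxicity is ≤33" (per cent).
- The allocation when a patient enters: "The highest dose level that is tolerable will be allocated".
- The transition: "a conventional three-at-one [44] design will be used as long as no DLT is observed", and then "After the first DLT is observed, one additional patient will be enrolled at the same dose", before the logistic model sets the dose.

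No exception to the limit is written for the additional patient. A later sentence in the same paragraph words the criterion in the opposite direction, as the highest dose with a median probability of 33% or more.

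Elsewhere the plan describes allocation patient by patient. The synopsis says: "Dose modifications will utilize a modified CRM for each successive subject until an MTD or the maximal planned dose is reached". Section 4.1.1 says "the dose cohort size would be 1". In its Table 2, scenario S5 treats one subject at log dose 8.5 and the next at 8, and scenario S2 treats one at 9 and the next at 8.5.

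Other places do contemplate a second patient at the dose of a DLT. Section 4.1.2 bases its minimum accrual on two DLTs at dose level 1. Section 11.2 bases its minimum on DLTs in the first two patients. Section 4.1.1 steps down from the highest dose when a second toxicity is seen there.

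**The concern.** The first patient after a DLT is the point at which a dose-finding rule matters most. Here one sentence fixes that patient's dose without the model, while the same paragraph and Section 4.1.1 have the model choose it. If the updated model puts the dose just given above 33%, the two instructions cannot both be followed, and two statisticians reading different sections would dose the same patient differently. At stake are that patient's exposure and the primary endpoint, because the outcome feeds the dose estimate.

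**Working it through.** **Inputs.** Section 4.1.1: the relation of dose to toxicity "is assumed to follow a two-parameter logistic model". Table 1 starts the fit with log doses 4, 5, 6, 7.5, 9, 10, 12, 15 and r = 0.05, 0.10, 0.2, 0.5, 0.8, 0.9, 1, 1, each with n = 1 and weight 0.5. Real subjects have weight 1 (assumption: full weight). The limit is 0.33.

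**Formulas.** With d the log10 dose, P = 1/(1 + exp(−β(d − d50))). Maximise Σ w[r ln P + (1 − r) ln(1 − P)]. The 33% dose is d50 + ln(0.33/0.67)/β.

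**The plan's own figure.** The Table 1 fit gives β = 0.919 and d50 = 7.461. The 33% dose is 7.461 − 0.708/0.919 = 6.691; at a target of 1/3 it is 7.461 − 0.693/0.919 = 6.707. The plan prints 6.7842, so the figure is not reproduced exactly.

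The same fit does follow Table 2. Without DLTs the 33% doses after subjects 1 to 8 are 6.94, 7.23, 7.61, 7.96, 8.31, 8.54, 8.82 and 9.18. With the 1-log cap and rounding to 0.5 these give 6, 7, 7.5, 8, 8.5, 8.5, 9, 9; only subject 6 differs (the table has 8). It also gives the drops in S5 (8.07, rounds to 8) and S2 (8.40, rounds to 8.5) if the DLT was in the single subject at the higher dose. The cell shading is lost, so that is an inference. The fit is close enough to test the point, but approximate.

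**One patient per step (Section 4.1.1).** Example, first DLT in subject 8 at log dose 9: β = 1.625, d50 = 8.837, so P(9) = 1/(1 + exp(−1.625 × 0.163)) = 0.57, and the 33% dose is 8.837 − 0.708/1.625 = 8.40.

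| First DLT in subject | Log dose given | P before the DLT | P after the DLT | 33% dose | Rounded to 0.5, maximum 9 |
|---|---|---|---|---|---|
| 1 | 5 | 0.09 | 0.44 | 3.91 | 4 |
| 2 | 6 | 0.15 | 0.41 | 5.61 | 5.5 |
| 3 | 7 | 0.27 | 0.52 | 6.40 | 6.5 |
| 4 | 7.5 | 0.30 | 0.52 | 6.96 | 7 |
| 5 | 8 | 0.34 | 0.55 | 7.43 | 7.5 |
| 6 | 8 | 0.25 | 0.41 | 7.74 | 7.5 |
| 7 | 8.5 | 0.32 | 0.50 | 8.07 | 8 |
| 8 | 9 | 0.38 | 0.57 | 8.40 | 8.5 |
| 9 | 9 | 0.29 | 0.43 | 8.67 | 8.5 |
| 10 | 9 | 0.24 | 0.36 | 8.90 | 9 |
| 11 | 9 | 0.20 | 0.31 | 9.10 | 9 |
| 12 | 9 | 0.18 | 0.27 | 9.26 | 9 |

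The model dose after rounding is below the dose just given for subjects 1 to 9. Subject 6 sits on the rounding boundary: a target of 1/3 gives 7.75.

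**Three per level (Section 11, read as cohorts of three at 1-log levels).** P at the dose after a first DLT in the 1st / 2nd / 3rd patient at the level:

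| Log dose | 1st | 2nd | 3rd |
|---|---|---|---|
| 5 | 0.44 | 0.32 | 0.25 |
| 6 | 0.32 | 0.26 | 0.22 |
| 7 | 0.45 | 0.33 | 0.27 |
| 8 | 0.60 | 0.42 | 0.33 |
| 9 | 0.66 | 0.47 | 0.38 |

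Seven of 15 are clearly above 33%. The third patient at 8 is at the limit (0.332), and the second at 7 is just below it (0.328).

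**Sensitivity.** Section 4.1.1 gives the d90 points a weight of one tenth, Table 1 gives 0.5, and the four seed patients' doses and outcomes are not stated. I crossed weights 0.1, 0.5 and 1 (all Table 1 rows) with no seeds or four assumed DLT-free seeds (all at log 5; two each at 5 and 6; one each at 5, 6, 7, 8).

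- First patient at 10^8, 10^8.5 or 10^9, one-patient path: 0.39 to 0.77 in all 12 combinations.
- First DLT in subject 1 at 10^5: 0.78, 0.44 and 0.31 at the three weights without seeds, but 0.15 to 0.22 with any of the seed sets.
- Subjects 11 and 12, no seeds: 0.31 and 0.27 at weight 0.5, but 0.38 and 0.35 at weight 1.

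**The case against.** The strongest reply is that Section 11 describes a sequence: three per level until a DLT, one more patient at that dose, then the model. A specific transition rule ahead of model-based allocation is a legitimate design choice. Sections 4.1.1, 4.1.2 and 11.2 all foresee a second patient at a DLT dose. Nor is 33% applied as a strict cap: Section 4.1.1 calls it an approximate target, a later Section 11 sentence reverses the inequality, and the refit already gives 0.38 for the first patient at 10^9 before any DLT. Investigators may depart from the model dose, and the DSMB may interrupt enrollment at any time.

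Much of this stands. It shows that deleting one sentence would not make the plan consistent, and that part of the excess at the top dose predates the DLT. It does not remove the conflict. The allocation sentence applies when a patient enters and carries no exception, and the synopsis, the cohort size and Table 2's S2 and S5 point to a different next dose. The other safeguards do not clearly cover this patient. The dose review in Section 4.2 concerns moving to the next level. Most halting rules in Section 4.5 need two toxicities, a treatment-related death being the exception. Section 4.1.1 explains investigator discretion by large increases in dose.

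A reader might infer that the model always puts the dose above 33% after a first DLT, so that Section 11 forbids its own repeat patient outright. The documents do not support that: 8 of 15 positions on the three-per-level path are at or below about 33%, as are late first DLTs at 10^9 in the base fit. A reader might also take a DLT in the first subject at 10^5 as the decisive case, because the 33% dose then falls to about 10^3.9, below the 10^4 level at which Section 11 ends the trial. That rests on leaving out the seed patients, whom Section 4.1.2 expects to be used.

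**Conclusion.** The plan gives conflicting instructions for the first patient after a DLT, and that follows from the text alone. How often the conflict takes effect depends on the path and on when the DLT occurs. It takes effect for an early first DLT with one patient per step, and for a DLT in the first patient at most levels with three per level. It is robust to prior weight and assumed DLT-free seeds only for the first patient at 10^8 to 10^9 on the one-patient path. At 10^5 it disappears once DLT-free seeds are included.

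The figures rest on a maximum-likelihood refit that does not exactly reproduce 6.7842 and that stands in for the posterior of Section 11, and on assumed seed data. They show size and direction; they are not the plan's exact model output. Because this is an operative allocation rule and can be settled in text, it should be resolved before another patient is dosed.

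**What to change.** Reconcile these places so that a single stated rule governs the first patient after a DLT:

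- the synopsis (CRM for each successive subject);
- Section 4.1.1 with Tables 1 and 2 (cohort size, prior weights, the second-toxicity rule at the highest dose);
- Section 4.1.2 and Section 11.2 (the assumptions behind minimum accrual);
- Section 11 (the repeat patient, the ≤33% allocation, and the sentence that words the criterion as 33% or more).

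If the repeat patient is kept, declare it an explicit exception to the ≤33% allocation and report the fitted DLT probability at that dose to the DSMB. Which rule stands is for the sponsor and the DSMB. The cost is a text amendment to several sections, with no extra patients or procedures.

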11.1 Study Design/Endpoints

This study is an open-label, dose escalating phase 1 study of the safety of intracranial administration of

M032, a genetically engineered HSV-1 expressing IL-12. For this reason, the primary endpoints of this study is to determine the safety and tolerability of a single 12 hour stereotactic intracerebral infusion of escalating doses of M032 virus, and to determine the maximally tolerated dose (MTD) of M032. The dose escalation scheme and the definition of the MTD are found in **Section 4.2**. Because M032 is administered as a single dose (although that single dose may be delivered via different catheters), intra-patient dose escalations will not be feasible.

Demographic Analysis: Demographic and baseline characteristics will be summarized for each cohort using the statistics of number, mean, median and range for continuous variables and for discrete factors, values will be tabulated.

Safety Analysis: Descriptive statistics will be used in the reporting of adverse events. Adverse events will be tabulated and frequencies of events will be determined. All events with a toxicity of Grade 3 or above (except as discussed in section 4.2) will be tabulated by event, as well as tabulations for all events (where toxicity is defined by the CTCAE, version 4.0). Laboratory analyses (chemistries, hematology, urinalysis, serological/immunological analyses, WBC and differential) will consist of measurements of change from baseline over time by patient and overall, with plots of actual values compared to normal values for patients by dose group. Logarithmic transformations may be applied as necessary. Group means and standard errors will be calculated for the various laboratory parameters. Concurrent Illnesses will be listed and examined by univariate and multivariable analysis as possible confounders in the treatment response relationship. Concurrent medications will also be listed. Effects of previous treatments for cancer will also be examined by univariate and multivariable analysis, and any potential related side effects will be analyzed and discussed.

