4.2 Definition of Dose-Limiting Toxicity

The Cancer Therapy Evaluation Program (CTEP) has published Common Terminology Criteria for Adverse Events, version 4.0 for the grading of adverse events experienced in clinical trials for anti-neoplastic agents. Any grade 3 or greater non hematologic toxicity as defined by NCI CTCAE v 4, and considered as being possibly, probably or likely related to M032 will be considered a Dose Limiting Toxicity (DLT). However, specific symptoms including seizures, neurologic deficits such as weakness, dysphasia or sensory loss are prominent in this patient population due to the fact that these tumors frequently disrupt the function of normal areas of eloquent brain. Neurologic symptoms from involvement of eloquent brain are commonplace; corticosteroid, radiation, and chemotherapies also produce pre-existing symptoms in almost all cases. The pre-existing conditions listed in the **Table** on the following page are acceptable for inclusion in the clinical trial, provided the subjects meet the other inclusion and exclusion criteria.

For all of these pre-existing conditions, DLTs will be defined as progressive involvement of neurological dysfunction not attributable to tumor progression and/or the development of life threatening symptomatology associated with the original baseline status.

Neurologic deterioration will not be considered dose-limiting if it resolves back to the patient's baseline within two weeks of completing treatment. For example, increased weakness or aphasia that occurs during the infusion will be treated with increasing steroid doses and/or slowing of infusion rates, but not treated as a DLT if symptoms improve to baseline within fourteen days of completing treatment. Because of the site of M032 inoculation, important additional events that will be considered dose-limiting toxicities if they are likely related to M032 include death, stroke, hematoma requiring surgery, untreatable neurologic deterioration, unresponsive systemic infection, and disseminated HSV infection.

Management of the above adverse events is outlined in **Section 5**.

The maximally tolerated dose (MTD) is the highest dose level below the maximally administered dose when dose escalation decisions are made according to the guidelines above. Enrollment will be stopped when the MTD is determined or the maximally planned dose is acceptably tolerated by six patients.

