10.1 Adverse Event Reporting (AE; formerly known as Adverse Drug Reaction)

10.1.1 Adverse Event

An adverse event (AE) is defined as any untoward medical occurrence associated with the use of a drug in humans, whether or not considered drug related. An AE can be any unfavorable and unintended sign (e.g., abnormal laboratory finding), symptom, or disease temporally associated with the use of a drug, without any judgment about causality. An AE can arise from any use of the drug and from any route of administration, formulation, or dose, including an overdose.

An illness or condition present at study entry is considered a pre-existing condition and will not be considered an AE unless the pre-existing condition worsens during the course of the study. This change may be considered an AE. An AE that occurs after signing informed consent but prior to the administration of study drug will be considered not related to study treatment.

AE's that have a grade increase to 4 or 5 will be considered an SAE and reported as required.

All AE's, irrespective of relationship to study drug, which occur or worsen after signing of consent form until 30 days after administration of study drug, must be reported and documented on the AE Case

Report Form (CRF). All medications given for an AE will be reported on the Concomitant Medication CRF.

Hospitalizations that are expected due to the disease and those that are unrelated to the study drug or disease will be reported as AE’s unless it meets the requirements for a serious adverse event (SAE) which can be found in Section 10.1.2. Hospitalizations due to merely diagnostic reasons, examinations as a matter of routine or planned surgery and due to social indication do not represent a hospitalization in the sense of the term “serious”.

An AE is considered unexpected if it is not listed in **Section 5.1**.

10.1.2 Serious Adverse Event Expedited Reporting Guidelines – Phase 1 studies with investigational agents:

A serious adverse event (SAE) is defined as:

- Unexpected AE
 - For grade 1, no expedited reporting required
 - For grade 2, the investigator will be unbiased in assessing the relationship of the event and test article and discuss the possible relatedness to treatment with the Medical Monitor. If found to be possibly, probably or definitely related to study drug, an expedited report will be submitted within 7 working days.

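### Section 11.1 filters the Grade 3-or-above adverse event table through the dose-limiting toxicity exemptions of Section 4.2, so the severity of some reversible neurologic events may not be visible

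*Combined protocol and SAP*

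**What the plan says.** Section 11.1 (Safety Analysis) makes three statements about adverse event tables.

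- A general one: "Adverse events will be tabulated and frequencies of events will be determined".
- One on severe events, with an exception: "All events with a toxicity of Grade 3 or above (except as discussed in section 4.2) will be tabulated by event".
- One that completes the same sentence, with no exception: "as well as tabulations for all events (where toxicity is defined by the CTCAE, version 4.0").

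Section 4.2, to which the exception points, sets out what counts as a DLT. Its base rule is "Any grade 3 or greater non hematologic toxicity as defined by NCI CTCAE v 4", if at least possibly related to M032. Two provisions then narrow it.

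- **Reversible neurologic events.** "Neurologic deterioration will not be considered dose-limiting if it resolves back to the" patient's baseline within two weeks of completing treatment. The example given is weakness or aphasia during the infusion.
- **Listed pre-existing conditions.** "For all of these pre-existing conditions, DLTs will be defined as progressive involvement of neurological dysfunction not attributable to tumor progression", and/or as life-threatening symptoms associated with the baseline status.

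On collection, Section 10.1.1 requires the case report form to record all adverse events "irrespective of relationship to study drug, which occur or worsen after signing of consent form", until 30 days after dosing. It also says that a condition present at entry is not an adverse event unless it worsens.

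**The concern.** A DLT definition and a severity table answer different questions. The first decides which events steer the dose. The second reports which severe events happened. A reversible severe deficit may reasonably be kept out of the first, but it is still tolerability information and belongs in the second.

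This matters here for three reasons. Safety and tolerability are part of the primary objective (Section 1.2). Section 4.2 itself describes neurologic symptoms as common in these patients, and Section 5.1 lists hemiplegia, headache, seizure and stroke among the expected events. Finally, the related virus G207 caused no DLT (Section 5.1), and Section 4.1.1 allows that no maximum tolerated dose may be reached. If DLTs are few, the Grade 3-or-above table carries much of the information on severe toxicity.

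Section 2.1 shows the kind of event at issue. In the split-dose G207 study, after a protocol deviation, one patient had twelve hours of mental status change and contralateral paresis and recovered quickly. No grade is given. An event of that course at Grade 3 or above would meet the two-week exemption here.

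**Working it through.** The plan states no figure for this table, so the check is of the text.

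**Step 1: what the exception could mean.** Three readings are possible.

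- *Narrow:* only deficits already present at baseline and unchanged.
- *Middle:* the two narrowing provisions of Section 4.2 (reversible neurologic events; listed pre-existing conditions).
- *Broad:* any Grade 3-or-above event that is not a DLT.

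**Step 2: what each reading does to the Grade 3-or-above table.**

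| Grade 3-or-above finding | Narrow | Middle | Broad |
|---|---|---|---|
| Unchanged baseline deficit | not an adverse event (10.1.1) | same | same |
| Neurologic event, back to baseline within two weeks | in | out | out |
| Worsening of a listed pre-existing condition, not counted as a DLT | in | possibly out | out |
| Hematologic event, or event unrelated to M032 | in | in | out |
| DLT | in | in | in |

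On every reading, all rows that are adverse events remain in the all-events tabulation.

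**Step 3: is the narrow reading enough to make the text harmless?** It would make the parenthesis redundant, because Section 10.1.1 already keeps unchanged pre-existing conditions out of the adverse events. The parenthesis changes the table only on the middle or broad reading, and both of those remove events that occurred.

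**Step 4: reach of the list.** The Section 4.2 table has 1 gait term + 4 muscle weakness terms + 9 nervous system terms = 14 CTCAE terms. They include seizure, headache, ataxia, stroke and central nervous system necrosis. The provision applies to them as pre-existing conditions, and progressive dysfunction not attributable to tumor progression, or life-threatening symptoms, still count as DLTs.

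**Step 5: are the data there?** The exemption window is 14 days after completing treatment and case report form collection runs to 30 days after dosing, so the exempted events are recorded.

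**Step 6: scale, by illustration only.** With 20 patients, each one left out lowers the reported frequency by 1/20 = 5 percentage points; with the synopsis maximum of 24, by 1/24 = 4.2 points. Suppose, as an assumption, that 3 of 20 had Grade 3 weakness or aphasia that resolved within 14 days and that no other Grade 3-or-above event occurred. The full count is 3/20 = 15% (exact 95% interval 3.2% to 37.9%). The filtered table would show 0/20, with an exact upper limit of 1 − 0.025^(1/20) = 16.8%. The documents give no expected rate for such events, and the plan calls only for descriptive statistics.

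**The case against.** The best defence has four parts.

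- **The events are not lost.** The same sentence of Section 11.1 adds a tabulation of all events without exception, and its mention of CTCAE makes a graded table plausible. The first half stands in full. The second is only plausible, since no grade breakdown is stated.
- **The narrow reading is natural.** Much of Section 4.2 concerns pre-existing conditions, and Section 5.3 allows for a subject whose baseline is Grade 3. This stands as a possible intention, but it makes the parenthesis unnecessary and so does not argue for keeping it.
- **Oversight does not rest on this table.** The monitoring board reviews all adverse events (Section 10.2), and the halting rules in Section 4.5 count Grade 3 and Grade 4 events under their own filters, without the two-week exemption. Escalation and the maximum tolerated dose are untouched. All of this stands, and it limits the point to reporting.
- **The exemptions are conditional.** Stroke, death and other named events remain dose-limiting if likely related to M032. This also stands.

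A reader might go further and infer that severe neurologic events vanish from the trial's main safety table, that the table would almost duplicate the DLT count, or that all 14 terms are removed outright. The documents do not support these. No table is called the main one. Near-duplication needs the broad reading, which treats the non-hematologic and relatedness limits as exceptions when they are parts of the base DLT definition. The 14 terms are handled separately only as pre-existing conditions.

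**Conclusion.** The point holds in a limited form. Section 11.1 imports DLT exemptions into a descriptive severity table. Following the text can leave a Grade 3-or-above neurologic event that resolves within two weeks out of that table, and possibly worsening of a listed pre-existing condition that was not counted as a DLT. Such events remain in the all-events tabulation, where their severity may not be visible.

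The severity is moderate. The conclusion assumes that the parenthesis is meant to have some effect, as it has none on the narrow reading, and that the all-events tabulation is not broken down by grade, on which the plan is silent. How many events would be affected cannot be derived from the documents. The primary dose-finding result does not depend on it.

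**What to change.** Delete the parenthesis in Section 11.1 that refers to Section 4.2. State instead that every Grade 3-or-above adverse event is tabulated by CTCAE term, grade, dose level and attribution, whether or not it was a DLT. Add one flag for DLT yes/no and one for any Section 4.2 exemption applied. Settle this before the analysis, so that the content of the table does not depend on how the cross-reference is read.

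The cost is one edit to the text and two columns in a table. The events are already collected, and the DLT decision already requires the exemption to be judged. The DLT definition, dose escalation and clinical management stay as they are. The only downside is that the reported frequency of severe events may be higher.
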